#### **4. STUDY ENROLLMENT**

##### **4.1 Recruitment and screening**

Subjects will be recruited through the Transfusion Medicine or Hematology Consult services at Washington University and up to 5 additional sites. A potentially eligible subject will be identified by his or her physician. Once a potentially eligible subject is identified, and after the treating staff has obtained permission from the subject to be contacted, a member of the study staff will contact the subject, describe the study, and obtain consent.

After signing the consent form the subject will be assigned a study ID number and study staff will determine if the subject is eligible based on his or her medical history and laboratory results. A subject is considered enrolled in the study after the informed consent document is signed by the subject and the subject meets all eligibility criteria. Within one day (Monday-Friday) after enrollment, the site should submit a copy of the Inclusion/Exclusion Criteria Checklist that has been signed by a site investigator to the Washington University Clinical Coordinating Center.

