## 9. STATISTICAL CONSIDERATIONS

### 9.1 Sample Size and Power

Review of 40 patients with TTP at BJH who would have met the inclusion criteria indicates that the composite primary endpoint rate was 55% in this historical group. Assuming a 10 percent of composite primary endpoint rate in the treated group and 40 historical controls, 14 treated patients are needed to have a 90% power to detect a 45 % difference in the incidence of exacerbation at the 5% significance level. We will enroll 20 patients total and expect to enroll 12 patients per year. Therefore, recruitment may be complete within less than 2 years. The time would be reduced by participation of other regional hospitals.

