### 9.2 Data analysis

Fisher Exact tests will be used to compare the incidence of the composite primary endpoint, Durable Treatment Response, Relapse, treatment-related adverse events and 4-week, 1-year and 2-year incidence of death between the treated group and historical controls. We will consider Chi-Square test to examine differences in the type and severity of adverse events between the treated group and historical controls.

The time to Durable Treatment Response and Relapse will be described by Kaplan-Meier estimators and log rank tests. The effects of patient characteristics will be evaluated with Cox proportional hazards models. Numbers of plasma exchanges to Durable Treatment Response will be compared with non-parametric tests (e.g. Kruskal-Wallis analysis of variance).

The value of ADAMTS13 biomarker data for predicting Exacerbation, Durable Treatment Response or Relapse will be analyzed by logistic regression. The relationship between ADAMTS13 biomarker parameters and platelet count, LDH or B cell levels will be investigated with linear regression models.

Rituximab levels and the extent of B cell depletion will be analyzed as stratified categorical data with Cochran-Mantel-Haenszel statistics.

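### Treated subjects may come from up to six sites but all 40 controls come from one hospital, and the primary test ignores site, so for outside subjects a site difference cannot be separated from a rituximab effect

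*Combined protocol and SAP*

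**What the plan says.** Section 4.1 of the combined protocol and SAP: "Subjects will be recruited through the Transfusion Medicine or Hematology Consult services at Washington University and up to 5 additional sites". No expected share, minimum or cap per site is given.

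Section 9.1 takes its control rate of 55% from a "Review of 40 patients with TTP at BJH who would have met the inclusion criteria", and no other controls are described. On accrual it says "We will enroll 20 patients total and expect to enroll 12 patients per year", and then "The time would be reduced by participation of other regional hospitals".

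Section 9.2 sets the primary analysis: "Fisher Exact tests will be used to compare the incidence of the composite primary endpoint, Durable Treatment Response, Relapse, treatment-related adverse events". There is no site term, site stratum or same-site comparison for the composite. The Cox models in that section concern patient characteristics and sit with the time-to-event outcomes. The Cochran-Mantel-Haenszel analysis concerns rituximab levels and B-cell depletion only.

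**The concern.** A subject treated outside BJH is compared with another hospital's past rate. For that subject, hospital and treatment change together, and enrolling more such subjects does not separate them.

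The protocol leaves some room for practice to differ. Section 5.2.1 accepts more than one replacement fluid, section 5.2.2 lets the clinician speed up the steroid taper, and Table 1 only suggests a taper. Exacerbation, one part of the composite, is counted in the 30 days after plasma exchange stops, when the taper is running. The documents do not show that these choices change the composite rate, nor do they rule it out.

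At stake is the reading of the pooled result. A lower background rate at the outside sites would look like benefit, and a higher one would mask benefit. The documents do not indicate which is more likely.

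**Working it through.** **Inputs.** From section 9.1: 40 controls at 55% (22/40), an assumed treated rate of 10%, 14 treated needed for 90% power at the 5% level, and 20 to be enrolled. From section 9.2: Fisher's exact test. The plan does not state sidedness; two-sided is assumed. It gives no outside-site rates and no site shares, so both are varied below.

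**The plan's own figure.** Pooled-variance normal approximation with 14 treated and 40 controls:
- pooled rate = (14 × 0.10 + 40 × 0.55)/54 = 0.433
- SE under the null = √[0.433 × 0.567 × (1/14 + 1/40)] = 0.154
- SE under the alternative = √[0.10 × 0.90/14 + 0.55 × 0.45/40] = 0.112
- power = Φ[(0.45 − 1.96 × 0.154)/0.112] = 90.7%

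Thirteen treated give 88.8%, so the stated 14 reproduces. Under the planned two-sided Fisher test, power is 84.2% with 14 and 94.8% with the 20 to be enrolled. Sample size is therefore not the problem here.

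**False benefit from a site difference.** Assume no drug effect. Let k of the 20 treated come from outside sites with background rate q, and the other 20 − k from BJH at 55%. Treated events are Bin(20 − k, 0.55) + Bin(k, q), and control events are Bin(40, 0.55). The expected spurious difference is (k/20) × (0.55 − q). The probability of two-sided Fisher p ≤ 0.05 with the treated rate lower, by exact enumeration:

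| Outside subjects (k of 20) | Spurious difference, q = 40% | Significant benefit, q = 40% | Spurious difference, q = 30% | Significant benefit, q = 30% |
|---|---|---|---|---|
| 0 | 0 points | 1.5% | 0 points | 1.5% |
| 5 | 3.75 points | 2.8% | 6.25 points | 4.0% |
| 10 | 7.5 points | 4.9% | 12.5 points | 9.4% |
| 16 | 12 points | 9.2% | 20 points | 22.8% |

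The benchmark for these one-direction figures is the 1.5% in the first row; counting both directions, it is 3.0%. A site difference need not produce the full planned 45-point gap: 5/20 against 22/40 gives p = 0.032, while 6/20 gives p = 0.10.

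**The opposite direction.** Going from 55% to 10% is an odds ratio of (0.10/0.90)/(0.55/0.45) = 0.091. Apply it to an outside background rate of 65% or 75%, and the treated rate there becomes 14.4% or 21.4%. If all 20 came from such sites, the extreme case, power falls from 94.8% to 86.2% or 65.3%.

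**Random variation between sites.** Let site rates follow a beta distribution with mean 55%, and assume an intraclass correlation of 0.05. By simulation, the two-sided error is 8.5% with six near-equal sites (4 subjects at BJH), of which 4.6% favours rituximab. It is about 5.2% with 10 of 20 at BJH, 4.5% with 12 and 4.1% with 15.

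**The case against.** The accrual plan points to a modest outside share. Section 9.1 projects 12 patients a year and treats other hospitals as a way to finish sooner, and up to five sites is a ceiling. If 15 of 20 come from BJH, a false favourable result stays at or below 4.0% even at an outside rate of 30%. This stands, and it limits the size of the problem. It does not remove it, because the plan fixes no share.

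Treatment is also partly standardised: plasma-exchange target, prednisone dose, stopping rule and a confirmed platelet trigger for exacerbation. The permitted variation is largely clinician choice or product availability, which can vary within BJH too. An intraclass correlation of 0.05 is wide: it puts 95% of site rates between 33% and 76%. These points also stand.

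A reader might infer that the primary test runs at 8.5% error. The documents do not support that. The figure needs both the assumed correlation and a 4-of-20 share at BJH that nothing in the plan suggests, and it counts errors in both directions.

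Finally, this is a declared pilot with openly historical controls. That is fair, but differences in period and chart selection affect all 20 subjects, whereas site affects only the outside ones and can be partly examined with data the trial will hold.

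**Conclusion.** The point holds, with minor to moderate importance. The primary comparison pools subjects from up to six sites against controls from one hospital and has no means of showing whether site contributed. For non-BJH subjects, site and treatment are confounded, in an unknown direction.

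The size is conditional on the outside share and on outside background rates, neither of which is in the documents. Over the assumed rates of 40% and 30%, a false favourable result ranges from 2.8% to 4.0% with 5 of 20 from outside, up to 9.2% to 22.8% with 16 of 20.

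Two stronger readings are tempting. One is that a significant result could not be credited to rituximab at all. The documents show no actual site difference and no dominant outside share, so that goes too far. The other is that stratifying the Fisher comparison by site would cure the problem. It would not: the outside sites have no controls, so their strata would contribute nothing.

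**What to change.** In section 9.2:

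1. Keep the pooled Fisher test as the primary analysis.
2. Prespecify a supporting same-site estimate of the composite: subjects enrolled at Washington University/BJH against the 40 BJH controls, as a difference in proportions with an exact 95% confidence interval. This assumes BJH is Washington University's hospital, as sections 2.1 and 2.2 suggest; the text should say so.
3. Tabulate the treated composite rate, with numerators and denominators, for BJH and non-BJH subjects.
4. Report the pooled result beside both, and state that the non-BJH comparison is confounded with site.

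The same-site estimate should not be a second significance requirement. Nor should attribution depend on its agreeing in size with the pooled estimate, since no margin for agreement could be justified at these numbers.

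The cost is one paragraph and one table from data already collected, with no extra patients. The downside is precision: two-sided Fisher power at 10% against 55% is 75% with 10 BJH subjects and 83% with 12, and it reaches 90% only at about 16. The same-site comparison also leaves period and selection differences in the historical controls untouched.

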### 1.2 Secondary Endpoints

#### 1.2.1 Clinical and Safety Endpoints

- Incidence of Durable Treatment Response
- Number of days to Durable Treatment Response
- Number of plasma exchanges to Durable Treatment Response
- Incidence of relapse
- Numbers of days to relapse
- 4 week, 1 year and 2 year incidence of death
- Incidence, type and severity of treatment-related adverse events

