#### **8.2. Off study criteria**

- 1) Death
- 2) Lost to follow up
- 3) Participation in other trials of investigational therapies

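### One- and 2-year death are tested by Fisher's exact test with no rule for unknown vital status, so the mortality estimates, and the comparison if loss differs, may be biased.

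*Combined protocol and SAP*

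**What the plan says.** Section 1.2.1 lists "4 week, 1 year and 2 year incidence of death" among the secondary endpoints. Section 9.2 opens with "Fisher Exact tests will be used to compare the incidence of the composite primary endpoint", and the same sentence extends that test to "4-week, 1-year and 2-year incidence of death between the treated group and historical controls". The next paragraph of 9.2 reads "The time to Durable Treatment Response and Relapse will be described by Kaplan-Meier estimators and log rank tests". Death is not in that sentence, and no other part of the plan gives it a method that allows for censoring.

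Section 8.2 gives three reasons for leaving the study. Besides death they are "Lost to follow up" and "Participation in other trials of investigational therapies". No loss rate is assumed, and there is no rule for classifying a patient whose status at 1 or 2 years is unknown.

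The comparison group is described in Section 9.1 as a "Review of 40 patients with TTP at BJH who would have met the inclusion criteria". The only outcome reported for it is that "the composite primary endpoint rate was 55% in this historical group". Its length of follow-up, source of vital status and completeness are not given.

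**The concern.** A Fisher table at 2 years has two columns, dead and alive. A patient last seen alive at month 8 belongs in neither, so the analyst must count that patient as a survivor or leave the patient out. Leaving lost patients out keeps every death seen before loss but removes people who were alive when last seen, which pushes the estimate up. Counting them as alive misses any death after loss, which pushes it down. The plan does not say which applies, so the choice could be made after the data are seen.

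The treated subjects have clinical status recorded every 3 months for 2 years (Section 6.1.5, Table 4). The controls are historical. If vital status is less complete in the controls, the two handlings err in opposite directions: dropping lost patients favours rituximab, and counting them as alive disfavours it. The plan already names a suitable method for relapse, so leaving death out is also inconsistent within 9.2.

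**Working it through.** **The plan's own figure.** No sample size or power is given for death. The only figure, 14 treated patients, concerns the composite endpoint (10% against 55%, 40 controls, 5% level). It reproduces with a two-sided pooled normal approximation:

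- pooled rate = (14 × 0.10 + 40 × 0.55)/54 = 0.433
- null SE = √(0.433 × 0.567 × (1/14 + 1/40)) = 0.154
- alternative SE = √(0.09/14 + 0.2475/40) = 0.112
- z = (0.45 − 1.96 × 0.154)/0.112 = 1.32, so power is 0.907

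This does not bear on the point.

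**Inputs for the illustration (all assumed).** True 2-year mortality is q = 20% in both groups. This is suggested by the 80% survival with plasma exchange in Section 2.1, which is not stated as a 2-year figure. Loss by 2 years is L = 5% in treated and 30% in controls, and is unrelated to prognosis.

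**Constant hazards.** With hd = −ln(1 − q)/2 and hl = −ln(1 − L)/2:

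- observed deaths D = hd/(hd + hl) × [1 − (1 − q)(1 − L)]
- lost before death = hl/(hd + hl) × [1 − (1 − q)(1 − L)]
- mortality is D if lost patients count as alive, and D/(1 − lost) if they are dropped

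Here hd = 0.1116.

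- L = 5%: hl = 0.0256; D = 0.8131 × 0.24 = 19.5%; lost = 4.5%; dropped = 0.1951/0.9551 = 20.4%.
- L = 30%: hl = 0.1783; D = 0.3849 × 0.44 = 16.9%; lost = 27.1%; dropped = 0.1693/0.7293 = 23.2%.

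**Early deaths (all before any loss).** Counted as alive, mortality is 20% whatever the loss. Dropped, it is q/(1 − 0.80 × L): 0.20/0.96 = 20.8% and 0.20/0.76 = 26.3%.

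**Spurious difference, treated minus control (truth is 0):**

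| Timing of deaths | Lost counted alive | Lost dropped |
|---|---|---|
| Constant hazard | 19.5 − 16.9 = +2.6 | 20.4 − 23.2 = −2.8 |
| 80% early | 19.9 − 19.4 = +0.5 | 20.8 − 25.7 = −4.9 |
| All early | 0 | 20.8 − 26.3 = −5.5 |

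Over true risks of 10% to 30% and control loss of 20% to 40%, the difference runs from −9.6 points (80% of deaths early, dropped) to +5.4 (constant hazard, counted alive). If all deaths are early, the lower end is 0.30/0.965 − 0.30/0.72 = 31.1% − 41.7% = −10.6.

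**Equal loss.** With 30% loss in both groups the spurious difference is 0. Each group's constant-hazard estimate is still wrong: 16.9% or 23.2% instead of 20%.

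**Kaplan-Meier.** Under the same independent loss it recovers 20% in each group, a difference of 0.

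**Effect on the test.** These rates sum binomial probabilities over all tables with a two-sided Fisher p of 0.05 or less, at equal 20% true risk.

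- No loss, 20 against 40 patients: 3.5%.
- 5% against 30% loss, constant hazard: 4.3% counted alive; 3.5% dropped (about 19 against 29 patients).
- 5% against 30% loss, all deaths early, dropped (about 19 against 30): 4.2%.
- 5% against 40% loss, constant hazard, counted alive: 5.0%.
- 5% against 40% loss, all deaths early, dropped (about 19 against 27): 6.3%, the highest found.

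The sampling SD of the difference with complete data is √(0.16/20 + 0.16/40) = 11 points. Power for 5% against 20% mortality is 26%.

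**The case against.** A reader might infer that loss is unequal and that the mortality comparison is therefore biased. The documents do not support that. They give no loss rate for either group and say nothing about how the controls were followed or what care and contact they had. They say only that 40 patients were reviewed. With equal loss the spurious difference is zero.

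Loss among trial subjects may also be small. Sections 5.2.5 and 5.2.6 keep refractory and relapsed patients in follow-up for 2 years, and Section 7.4.1 collects serious adverse events, which include deaths, throughout. Among 20 subjects, 5% loss is one patient.

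A reader might also infer that any handling of lost patients gives a wrong incidence. That fails when deaths are early, because counting lost patients as alive is then nearly exact. Section 2.1 itself mentions early death in this disease, so the case is not remote.

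Nor do the figures suggest that a false conclusion about mortality is likely. The bias is small beside the sampling error, the rejection rate hardly moves, and death is one of several secondary endpoints in a pilot. The primary endpoint, settled by about day 60, is little affected. With complete vital status, Fisher's test at a fixed time is a valid exact choice when deaths are few.

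Finally, Kaplan-Meier is only a partial cure. It assumes that loss is unrelated to prognosis, and it does not recover deaths elsewhere that the review of controls missed.

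All of this stands, and it limits the point. It does not remove the gap: departure from follow-up is foreseen, no rule covers it, and in a pilot the mortality estimates and their intervals matter more than the p-value.

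**Conclusion.** The point holds as a gap in the analysis plan for a secondary endpoint. Fisher's test for 1- and 2-year death needs complete vital status, and the plan neither ensures it nor says what to do without it. If status is incomplete, each group's mortality estimate can be distorted. If loss also differs between groups, so can the comparison, in a direction set by the handling of lost patients.

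The size depends on assumptions that the documents cannot settle. With 20% true mortality and 5% against 30% loss, the spurious difference lies between about 0 and 5.5 points. More extreme assumptions reach about 10 points. The 4-week comparison is largely untouched, because status should be nearly complete by then. The change is worth making because it is cheap, not because the trial's main conclusion depends on it.

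**What to change.** In Section 9.2:

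- Estimate death at 4 weeks, 1 year and 2 years by Kaplan-Meier in both groups, from Day 1 (first plasma exchange), censored at the date last known alive, with confidence intervals.
- Compare the groups with one log-rank test, in an exact or permutation version if deaths are few. Fisher's test may stay for 4-week death.
- State the time origin explicitly. The Definitions start the 2-year Observation Period at the first Durable Treatment Response, while Table 4 counts 2 years from the first plasma exchange. The first origin cannot serve for death, since patients who die before responding would never enter.
- Report the number with known vital status in each group at each time point, and say how vital status was obtained for the controls.
- Add a best/worst-case sensitivity analysis for patients of unknown status, because loss may be related to prognosis.

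The cost is new wording in 9.2 and abstraction of the date of death or last contact for the 40 controls. No sample size changes.

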## 7. ADVERSE EVENT CRITERIA AND REPORTING

We will use the descriptive terminology developed by the National Cancer Institute for reporting adverse events (AEs): Common Toxicology Criteria for Adverse Events (CTC) version 4. 0 dated May 28 2009. The CTC includes a grading (severity) scale for each adverse event term. Grades were developed using the following guidelines:

- Grade 0 - No adverse event or within normal limits
- Grade 1 - Mild adverse event
- Grade 2 - Moderate adverse event
- Grade 3 - Severe adverse event
- Grade 4 - Life threatening or disabling adverse event
- Grade 5 - Death related to adverse event

In general, investigators are to report adverse events as diseases or syndromes whenever possible, instead of reporting individual component symptoms, signs, laboratory abnormalities, and sequel. The following types of occurrences are not considered adverse events and do not need to be reported: 1) pre-existing medical conditions that are present at the start of the study; and 2) previously scheduled hospitalizations and hospitalizations needed for diagnostic or elective surgical procedures for the management of pre-existing medical conditions.

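### Adverse-event severity is an ordered 0–5 grade, but the only test named for it, tentatively, is a chi-square that ignores the order, and the unit of analysis is not stated

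*Combined protocol and SAP*

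**What the plan says.** Section 1.2.1 lists among the secondary endpoints "Incidence, type and severity of treatment-related adverse events". Section 7 defines the measure: "The CTC includes a grading (severity) scale for each adverse event term". The scale starts at "Grade 0 - No adverse event or within normal limits" and ends at "Grade 5 - Death related to adverse event", which makes six ordered levels.

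Section 9.2 deals with type and severity in one sentence: "We will consider Chi-Square test to examine differences in the type and severity of adverse events between the treated group and historical controls". The incidence of treatment-related adverse events is handled separately, by Fisher exact test. The only non-parametric comparison named is for the number of plasma exchanges. Section 9.2 names no trend, rank or ordinal method for grade, and does not say whether a patient or an event is the unit.

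Section 9.1 gives the group sizes: "We will enroll 20 patients total and expect to enroll 12 patients per year", to be set against 40 historical controls. It gives no grade distribution, target difference or power for severity.

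**The concern.** The safety question about severity has a direction: is toxicity worse with rituximab added? A Pearson chi-square on grades 0 to 5 treats the grades as unordered labels and spreads its power over up to five degrees of freedom. It gives the same answer if the grade labels are shuffled. With 20 treated patients, a non-significant result from such a test would be weak reassurance about a shift to higher grades.

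The open unit adds a second problem. Section 7.4 collects all adverse events for one year, so one patient can contribute several. If events are tabulated as though independent, the test can reject too often. Leaving both test and unit open also means they could be chosen after the data are seen.

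**Working it through.** **1. The plan's own figure.** The only power statement is for the primary endpoint. Its inputs are "the composite primary endpoint rate was 55% in this historical group" and "Assuming a 10 percent of composite primary endpoint rate in the treated group and 40 historical controls", with a 5% level and 90% power. For p₁ = 0.10, p₀ = 0.55 and k = 40/14 = 2.857, the pooled rate is (0.10 + 2.857 × 0.55)/3.857 = 0.433. The usual two-sided formula without continuity correction is

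n₁ = [1.960·√((1 + 1/k)·0.433·0.567) + 1.282·√(0.10·0.90 + 0.55·0.45/k)]² / 0.45²

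= (1.129 + 0.539)² / 0.2025 ≈ 13.7, so 14 treated patients (power 90.7%). This agrees with section 9.1. It says nothing about severity, so everything on power below rests on assumed grade distributions.

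**2. Why order matters.** For the same signal (noncentrality 8) at the 5% level, a 1-df test has 80.7% power and a 5-df test 56.4%, a difference of 24.3 points. A consistent shift puts nearly all its signal into the one trend direction.

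**3. Power under a consistent shift.** Inputs: 20 vs 40 patients, worst grade per patient, two-sided 5%, 40,000 simulated trials per scenario. Four control distributions for grades 0 to 5 were assumed:

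- mild: 0.30, 0.30, 0.20, 0.12, 0.05, 0.03
- heavy: 0.10, 0.20, 0.30, 0.22, 0.12, 0.06
- uniform: 1/6 each
- sparse: 0.50, 0.25, 0.15, 0.07, 0.02, 0.01

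In the treated group the odds of being at or above each grade are multiplied by the odds ratio (OR). For example, in the mild case 20% of controls reach grade 3 or higher (odds 0.25). An OR of 3 gives odds 0.75, that is 0.75/1.75 = 43%.

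| OR | Chi-square | Wilcoxon | Gain (points) |
|---|---|---|---|
| 2 | 14–17% | 28–29% | 10–16 |
| 3 | 31–39% | 59–60% | 20–29 |
| 4 | 49–58% | 79–80% | 21–30 |
| 5 | 63–72% | 89–90% | 17–26 |

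The linear trend test gives nearly the same gains. When each test is calibrated to its true size, the gain is about 8 to 29 points.

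**4. Where the gain shrinks.** At OR 1.5 it is 4–6 points. At OR 2 to 5 it is 8–17 points with four levels and 4–10 with three.

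**5. Where it reverses.** Three control distributions were assumed: (0.20, 0.25, 0.25, 0.20, 0.07, 0.03), (0.40, 0.25, 0.20, 0.10, 0.03, 0.02) and uniform. Power is listed in that order, accurate to a point or two.

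| Change in treated group | Chi-square | Wilcoxon | Trend |
|---|---|---|---|
| Extra 20% of patients at grade 4 | 29/43/15% | 21/24/9% | 21/33/10% |
| Extra 30% at grade 4 | 53/70/30% | 38/44/15% | 41/58/16% |
| 80% of grade 0 moved to grade 1 | 21/64/18% | 6/26/6% | 6/15/5% |

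If the excess is spread over grades 3 to 5 instead, the trend test is modestly ahead: 19/29/8% against 13/21/7%.

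**6. Sparse cells.** The treated-row expected count is 20/60 = one third of the column total, so it is below 5 for any grade seen in fewer than 15 of the 60 patients. If all six grades occur, at most three columns can reach 15, because four would use all 60 patients. At least three treated cells therefore have expected counts below 5, whatever the distribution.

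**7. Events as the unit.** With 2 to 6 events per patient and within-patient correlation 0.1 to 0.3 (both assumed), the simulated chi-square type I error runs from 5.2% to 14.8%.

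**The case against.** The strongest case against has four parts.

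- **The wording is tentative and covers two things.** The chi-square is only to be considered, it suits type, and a trend version is not excluded. This stands. A reader might infer that the plan commits to an unordered test for severity, but the text does not go that far.
- **The power loss depends on a favourable alternative.** A proportional-odds shift is the pattern that rank tests detect best. The background and toxicity sections describe mostly mild infusion reactions plus discrete severe toxicities, and for single-grade excesses the chi-square does better (step 5). This stands as a limit on the size of the gain. It does not make an unordered test the better default for asking whether toxicity is worse, and a separate comparison of grade 3 or higher partly covers the gap.
- **Sparse cells do no visible harm.** The chi-square's simulated size was 3.5–4.6% under the four distributions in step 3, so it is mildly conservative. A reader might infer that low expected counts make it invalid; these figures do not show that.
- **Little depends on this test.** It is one secondary comparison in a pilot. Incidence and death have Fisher tests, serious events get expedited Medical Monitor review, and no decision rule uses the severity p-value. This stands and keeps the point minor.

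The controls also matter. Sections 7 and 7.4 describe grading and reporting for enrolled subjects. Nothing shows that the 40 historical patients have CTC grades.

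**Conclusion.** The point holds as a minor one. Severity is an ordered endpoint, the only test named for it ignores the order by default, and the unit is undefined. An order-using test gains about 10 to 30 points of power if toxicity shifts consistently to worse grades (OR 2 to 5), with worst grade per patient, six grades and 20 vs 40 patients. None of those shift or grade assumptions comes from the documents.

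Two stronger readings are not supported. The first is that the plan as written loses 10 to 30 points outright: the text is tentative, and other plausible patterns give a small gain or a reversal. The second is that the severity test will have an inflated false-positive rate: this requires events to be the unit, which section 9.2 does not say, and the rate depends on assumed event counts and correlation, with the low end near nominal.

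**What to change.** In section 9.2, separate severity from type and prespecify the following:

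- **Severity:** each patient's worst CTC grade over a stated window, compared by one named exact test, either linear trend (Cochran-Armitage, with grade scores) or Wilcoxon rank-sum. In step 5 the trend test generally loses less than Wilcoxon when the excess is at grade 4.
- **Alongside it:** the per-patient grade table by group, and a Fisher exact comparison of the proportion with grade 3 or higher.
- **Type:** unordered exact tests, with the patient as the unit.
- **Controls:** make the comparison only for historical patients whose records allow grading. Do not code an unrecorded event as grade 0, because under-recording would then look like a shift in toxicity.

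The cost is a few lines of text. No new data are needed for treated patients; for controls it depends on what the charts hold. There are two downsides. Worst grade hides repeated events, which should be listed descriptively. An ordered test loses power for non-monotone or single-grade excesses, which the grade 3 or higher comparison covers only in part: it would not detect added mild reactions.
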